#### **LIST OF IN-TEXT FIGURES**

**1.0**

**LIST OF ABBREVIATIONS**

ADT	antidepressant therapy
AE	adverse event
ALP	alkaline phosphatase
ALT	alanine aminotransferase
AST	aspartate aminotransferase
ATRQ	Antidepressant Treatment Response Questionnaire
BP	blood pressure
bpm	beats per minute

CI	confidence interval
CPK	creatine phosphokinase
CRF	case report form

DBTP	double-blind treatment period
ECG	electrocardiogram, electrocardiographic
eCRF	electronic case report form
EDC	electronic data capture

ET	early termination
GGT	gamma glutamyltransferase
HDL	high-density lipoprotein
ICF	informed consent form
IND	Investigational New Drug (application)
IP	investigational product
ITT	intent-to-treat
IV	intravenous
IWRS	interactive web response system
LDH	lactate dehydrogenase
LDL	low-density lipoprotein
LLN	lower limit of normal
MADRS	Montgomery-Åsberg Depression Rating Scale

MDD	major depressive disorder
mITT	modified Intent-to-Treat
NEAE	newly emergent adverse event
OLTP	open-label treatment period
PCS	potentially clinically significant
PID	patient identification
PK	pharmacokinetic
QTc	QT interval corrected for heart rate
QTcB	QT interval corrected for heart rate using the Bazett formula ( $QTcB = QT/[RR]^{1/2}$ )
QTcF	QT interval corrected for heart rate using the Fridericia formula ( $QTcF = QT/[RR]^{4/5}$ )
SAE	serious adverse event
SAP	Statistical Analysis Plan
SD	standard deviation
SFU	Safety Follow-up
SI	Le Système International d'Unités (International System of Units)
SOC	system organ class
TBL	total bilirubin
TEAE	treatment-emergent adverse event
TESAE	treatment-emergent serious adverse event
UDS	urine drug screen
ULN	upper limit of normal

## **2.0 INTRODUCTION**

This Statistical Analysis Plan (SAP) describes the methodology that will be used to summarize the statistical analyses of the efficacy and safety data for the final protocol Amendment 2 of Study RAP-MD-04 (version dated 13 Nov 2018).

Study RAP-MD-04 is a multicenter, double-blind, randomized, placebo-controlled, parallel-group study to evaluate the efficacy, safety, and tolerability of rapastinel as long-term maintenance treatment for patients with major depressive disorder (MDD) who completed 1 of the rapastinel lead-in studies (RAP-MD-01, RAP-MD-02, or RAP-MD-03). While the protocol was written to accommodate the potential recruitment of *de novo* patients, there were no *de novo* patients enrolled. Consequently, all analysis in this document pertains specifically to roll-over patients only.

The study will be conducted for the roll-over patients in the following periods:

- An 8- to 16-week, open-label treatment period (OLTP) where patients receive rapastinel 450 mg IV weekly
- A randomized, double-blind treatment period (DBTP) of at least 26 weeks (and up to 104 weeks) where patients are randomized 1:1:1 to either rapastinel 450 mg weekly, rapastinel 450 mg biweekly or placebo
- A 2-week safety follow-up period (for patients who do not enter the RAP-MD-06 extension study only)

In order for patients to transition from the OLTP and be randomized into the DBTP, the patient must meet the stable responder criterion sometime after 8 weeks (and up to 16 weeks) during the OLTP. A patient will be considered a stable responder upon achieving both criteria (1) and (2) below:

- 1) An observed Montgomery-Asberg Depression Rating Scale (MADRS) total score  $\leq 12$  with no more than one modest MADRS excursion (MADRS total score  $> 12$  but  $\leq 16$ ) for at least 6 consecutive weeks.
- 2) An observed MADRS total score  $\leq 12$  for at least 2 consecutive visits prior to randomization.

To meet these criteria a patient must have no missing MADRS assessments within the last 6 consecutive weeks prior to randomization.

The OLTP starts with the first dose of open-label treatment and ends with 1 of the following: the last scheduled assessment at the Visit 122/Early Termination for patients who do not enter the DBTP; the first dose of double-blind treatment for patients who enter the DBTP.

[figure not shown]
The double-blind treatment period starts when the first dose of double-blind treatment is administered and ends with the last scheduled assessment at Visit 122 (or ET).

[figure not shown]
For patients not entering RAP-MD-06, the safety follow-up (SFU) period starts after completion of the last scheduled assessment at Visit 122 (or ET) and ends with the last available assessment.

[figure not shown]
Individual treatment durations will vary, as patients enrolled early in the study will be allowed to continue treatment in the DBTP until a relapse occurs or the study is terminated. The maximum duration of the study will be 104 weeks (the study ends when all randomized patients have either met relapse criteria, early terminated for other reasons, or completed 26 weeks of the DBTP).

[figure not shown]
**RESTRICTED**

[figure not shown]

*RAP*

[figure not shown]
**RAP**

[figure not shown]
### **3.0 STUDY OBJECTIVES**

The objective of this study is to evaluate the efficacy, safety, and tolerability of rapastinel relative to placebo in the prevention of relapse in patients with MDD.

#### **Efficacy Objectives**

- **Primary efficacy objective:** To evaluate the efficacy of rapastinel (450 mg IV weekly or once every 2 weeks) versus placebo in the maintenance treatment of MDD as an adjunctive treatment to ongoing antidepressant therapy (ADT), as measured by time to relapse during the first 52 weeks of the DBTP
- **Secondary efficacy objective:** To evaluate the efficacy of rapastinel (450 mg IV weekly or once every 2 weeks) versus placebo in the maintenance treatment of MDD as an adjunctive treatment to ongoing ADT, as measured by time to relapse during the DBTP

**RESTRICTED**

#### **4.0 ANALYSIS POPULATIONS**

The following analysis populations will be considered in the statistical analysis of the study.

##### **4.1 OPEN-LABEL SAFETY POPULATION**

The Open-label Safety Population will consist of all patients who signed the informed consent form (ICF) and received at least 1 dose of open-label rapastinel during the OLTP of the study.

##### **4.2 OPEN-LABEL INTENT-TO-TREAT POPULATION**

The Open-label Intent-to-Treat (Open-label ITT) Population will consist of all patients in the Open-label Safety Population who had at least 1 postbaseline assessment of the MADRS during the OLTP of the study. An assessment is considered postbaseline in the OLTP if it was taken after the first dose of open-label rapastinel during the OLTP of the study.

##### **4.3 DOUBLE-BLIND SAFETY POPULATION**

The Double-blind Safety Population will consist of all patients in the Open-label Safety Population who were randomized to a treatment group during the DBTP of the study and received at least 1 dose of investigational product (IP) during the DBTP.

For by treatment analyses using the Double-blind Safety Population, patients will be assigned to the treatment groups they were randomized to during the DBTP.

##### **4.4 DOUBLE-BLIND MODIFIED INTENT-TO-TREAT POPULATION**

The Double-blind modified Intent-to-Treat (Double-blind mITT) Population will consist of all patients in the Double-blind Safety Population.

For by treatment analyses using the Double-blind mITT Population, patients will be assigned to the treatment groups that they were randomized to during the DBTP.

## **5.0 PATIENT DISPOSITION**

The number of patients in the Open-label Safety and Open-label ITT Populations will be summarized overall by study center. The number of patients in the Double-blind Safety Population and Double-blind mITT Population will be summarized overall, by treatment group, and by study center.

The number and percentage of patients who entered the OLTP, who prematurely discontinued from the OLTP, who completed the OLTP, who met or did not meet the criteria to enter the DBTP at the end of the OLTP, and who entered the SFU will be summarized overall and by reasons for premature discontinuation as recorded on the open-label disposition page of the electronic case report forms (eCRF) for the Open-label Safety Population.

Similarly, the number and percentage of patients who completed the DBTP, who prematurely discontinued from the DBTP, and who entered the SFU will be summarized overall, by double-blind treatment group, and by reasons for premature discontinuation as recorded on the double-blind disposition page of the eCRF for the Double-blind Safety Population.

## **5.1 PROTOCOL DEVIATIONS**

The number and percentage of patients with significant protocol deviations during the OLTP will be summarized overall in the Open-label Safety Population. Similarly, the number and percentage of patients with significant protocol deviations during the DBTP will be summarized overall and by double-blind treatment group in the Double-blind Safety Population. Protocol deviations will be defined in the Protocol Deviation Requirement Specification, including significance classification.

## **6.0**

### **DEMOGRAPHICS AND OTHER BASELINE CHARACTERISTICS**

Demographic parameters (eg, age, race, ethnicity, sex, weight, height, body mass index) and other baseline characteristics will be summarized overall for the Open-label ITT Population and by treatment group for the Double-blind mITT Population.

Medical and surgical history, psychiatric history, previous treatment with psychotropic medication, and nondrug psychiatric treatment will be summarized overall for the Open-label Safety Population and by treatment group for the Double-blind Safety Population.

Prior medication is defined as any medication started before the date of the first dose of open-label IP. Concomitant medication during the OLTP is defined as any medication taken on or after the date of the first dose of open-label IP during the OLTP. Concomitant medication during the DBTP is defined as any medication taken on or after the date of the first dose of double-blind IP during the DBTP.

The use of prior and concomitant medications during the OLTP will be summarized by the number and percentage of patients receiving each medication within each therapeutic class for the Open-label Safety Population. Concomitant medications during the DBTP will be summarized by treatment group by the number and percentage of patients receiving each medication within each therapeutic class for the Double-blind Safety Population. Multiple medication use of the same therapeutic class by a patient will only be counted once. Concomitant medications started after the patient's last study visit during their last treatment period will not be summarized but will be included in the data listings.

Prior ADT treatment in the current episode, as recorded on the ATRQ collected in the lead-in studies, will be summarized by frequency counts and percentages for patients who took each ADT in adequate dose and duration, total number of ADT taken at adequate dose and duration (ie, 1, 2, 3 or more), and percentage of improvement reported (ie, < 25%, 25% to 49%, 50% to 75%, or >75%). For the OLTP, the summaries will be overall for the Open-label Safety Population. For the DBTP, the summaries will be by treatment group for the Double-blind Safety Population.

The *WHO Drug Dictionary Enhanced* will be used to classify prior and concomitant medications by therapeutic class and drug name.

## **7.0 EXTENT OF EXPOSURE AND TREATMENT COMPLIANCE**

### **7.1 EXTENT OF EXPOSURE**

Exposure to open-label rapastinel for the Open-label Safety Population during the OLTP will be summarized for treatment duration, calculated as the number of days from the date of the first dose of open-label rapastinel taken to the date of the last dose taken during the OLTP, inclusive. Descriptive statistics will be presented.

Exposure to double-blind IP for the Double-blind Safety Population during the DBTP will be summarized for treatment duration, calculated as the number of days from the date of the first dose of double-blind IP taken to the date of the last dose taken during the DBTP, inclusive. Descriptive statistics will be presented by treatment group.

The number of IV doses of rapastinel administered to each patient during the OLTP will be summarized using descriptive statistics for the Open-label Safety Population.

Similarly, the number of IV doses administered to each patient during the DBTP will be summarized by treatment group, using descriptive statistics for the Double-Blind Safety Population.

The number and percentage of patients taking each qualifying ADT in the OLTP will be summarized for the Open-label ITT Population; the number and percentage of patients taking each qualifying ADT in the DBTP will be summarized by double-blind treatment group for the Double-Blind mITT Population. Mean daily dose and duration of previous treatment with each qualifying ADT will be summarized using descriptive statistics for the OLTP and by double-blind treatment group for the DBTP for the respective ITT or mITT populations.

### **7.2 MEASUREMENT OF TREATMENT COMPLIANCE**

*Dosing compliance* for a specified study period will be defined as the total number of IV doses actually received by a patient during that period divided by the number of IV doses that were expected to be received during that same period multiplied by 100. The total number of IV doses actually received during a specific time period is calculated as the sum of IV doses received during that period as obtained from the study medication record. The number of IV doses expected to be taken for a specific treatment period will be the number of weeks in that period, calculated as  $\lceil (period\ exit\ date - period\ entry\ date + 1)/7 \rceil$ .

Descriptive statistics for IP compliance will be presented overall for the OLTP and by treatment group for the DBTP using the respective safety populations.

Dosing compliance for the background ADT during a specified period is defined as the total dose actually taken by a patient during that period divided by the total dose expected to be taken during the same period multiplied by 100. The total ADT dose actually taken during a specific time period is calculated as the sum of ADT dose taken during that period as obtained from the study medication *Exposure: Background Antidepressant CRFs*. The total ADT dose expected to be taken for a specific treatment period will be obtained from the same CRFs. Descriptive statistics for ADT compliance will be presented overall for the OLTP and by treatment group for the DBTP using the respective ITT or mITT populations.

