**Table 15.2–1. Visit Time Windows for Screening and OLTP**

OLTP Visit Timepoint	Visit Number (AVTSIT)	Target Day for Rollover Patients Relative to the First IP Dose during the OLTP (ADY)	Window for Rollover Patients
Screening	Visit 1	1	1
Week 0	Visit 2	8	[2, 11]
Week 1	Visit 3	15	[12, 18]
Week 2	Visit 4	22	[19, 25]
Week 3	Visit 5	29	[26, 32]
Week 4	Visit 6	36	[33, 39]
Week 5	Visit 7	43	[40, 46]
Week 6	Visit 8	50	[47, 53] *
Week 7	Visit 9	57	[54, 60] *
Week 8	Visit 10	64	[61, 67] *
Week 9	Visit 11	71	[68, 74] *
Week 10	Visit 12	78	[75, 81] *
Week 11	Visit 13	85	[82, 88] *
Week 12	Visit 14	92	[89, 95] *

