**Table 15.2–1. Visit Time Windows for Screening and OLTP**

OLTP Visit Timepoint	Visit Number (AVISIT)	Target Day for Rollover Patients Relative to the First IP Dose during the OLTP (ADY)	Window for Rollover Patients
Week 13	Visit 15	99	[96, 102]*
Week 14	Visit 16	106	[93, 109]*
Week 15**	Visit 17	113	> 109*
Week 16	Visit 18		NA
Early Termination	Visit 122	NA	NA

\* If rollover patients meet stabilization criteria at Visits 9–17, Visit 18/Week 16 assessments should be completed at that visit.

\*\* Rollover patients who do not meet stability criteria by Visit 17/Week 15 will undergo the End-of-Treatment/Early Termination assessments (Visit 122/Week 104/ET, as shown on the DBTP Schedule of Evaluations).

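### For patients who go on to double-blind treatment, the compliance formula expects one open-label infusion more than can be given, so complete dosing scores 88.9% to 94.1% unless the transition is early

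*SAP*

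**What the plan says.** Section 7.2 of the SAP defines dosing compliance as infusions received in a period, divided by infusions expected in that period, times 100. For the denominator it states: "The number of IV doses expected to be taken for a specific treatment period will be the number of weeks in that period". The number of weeks is (period exit date − period entry date + 1)/7, shown in ceiling brackets, so any fraction is rounded up. Section 7.2 does not define the exit date.

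The boundaries are in Section 2:

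- Length and frequency: "An 8- to 16-week, open-label treatment period (OLTP) where patients receive rapastinel 450 mg IV weekly".
- Start of the open-label period (OLTP): "The OLTP starts with the first dose of open-label treatment and ends with 1 of the following".
- One of the possible ends: "the first dose of double-blind treatment for patients who enter the DBTP".
- Start of the double-blind period (DBTP): "The double-blind treatment period starts when the first dose of double-blind treatment is administered".

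Table 15.2–1 counts days from the first open-label dose. Visit 1 is Day 1, Visit 9 has target Day 57 and Visit 17 has target Day 113. Its footnote says that, for patients who meet the stabilization criteria at Visits 9 to 17, "Visit 18/Week 16 assessments should be completed at that visit". Table 15.2–2 puts Visit 18 at Day 0 relative to the first double-blind dose.

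**The concern.** The transition day closes one period and opens the next. The infusion given that day is the first double-blind dose, so it cannot be in the open-label numerator. The +1 nevertheless counts the day as part of the open-label period, and rounding up turns that single extra day into a whole extra expected infusion. A patient who keeps exactly to the schedule then cannot reach 100%.

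The reported figure would partly measure the calendar day of the transition rather than missed infusions. Two patients with identical, complete dosing score 100% or 88.9% depending on whether Visit 9 fell one day early or on its target day. A fully dosed patient on target (8/9 = 88.9%) looks much like one who missed an infusion and moved over a day early (7/8 = 87.5%). The shortfall is also largest for those who stabilize earliest.

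**Working it through.** **Inputs.** Entry is Day 1, the first open-label dose (Section 2). Exit is the day of the first double-blind dose (Section 2). Transition is at Visit v, v = 9 to 17, with target day 7(v − 1) + 1 (Table 15.2–1). Open-label infusions under perfect weekly dosing are given at Visits 1 to v − 1, so v − 1 in total.

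**The plan's own figure.** Target Days 57 and 113 lie 56 and 112 days after the first dose. 56/7 = 8 and 112/7 = 16, which agrees with the 8 to 16 weeks in Section 2 and with 8 to 16 weekly open-label infusions.

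**Section 7.2 formula.** Because entry is Day 1, (exit − entry + 1) equals the exit day, so expected infusions = ceiling(exit day/7).

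| Transition | Exit day | Expected | Possible | Compliance with perfect dosing |
|---|---|---|---|---|
| Visit 9, 1–3 days early | 54–56 | 8 | 8 | 100% |
| Visit 9, on target or 1–3 days late | 57–60 | 9 | 8 | 88.9% |
| Visit 13, on target or 1–3 days late | 85–88 | 13 | 12 | 92.3% |
| Visit 17, 1–3 days early | 110–112 | 16 | 16 | 100% |
| Visit 17, on target or 1–3 days late | 113–116 | 17 | 16 | 94.1% |

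The same pattern holds at all nine visits: (v − 1)/v on target or late, 100% when early. The excess arises on 4 of the 7 days from 3 days before to 3 days after target.

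**Average among perfectly dosed patients who enter the DBTP**, with equal weight on Visits 9 to 17 (an assumption):

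- All on target: the mean of (v − 1)/v over v = 9 to 17 is 0.920, or 92.0%.
- Transition days uniform within 3 days of target (a second assumption): 3/7 + (4/7) × 0.920 = 0.954, or 95.4%.

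The true value is 100% in both cases.

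**Would another reading of the formula repair it?**

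- *Exit on the day before the first double-blind dose* (the same as dropping the +1): Day 57 gives ceiling(56/7) = 8, which is right. Day 58 still gives ceiling(57/7) = 9 against 8.
- *Exit on the last open-label dose*: on target, ceiling(50/7) = 8 and ceiling(106/7) = 16, both right. If the eighth infusion is 1 to 3 days early (Days 47–49), the result is 7, and 8/7 = 114%.
- *Rounding down*: right on target and 1–3 days late. A transition on Day 54 or 55 gives 7, and 8/7 = 114%.
- *Counting the exit-day infusion in the numerator*: 9/9 on target, but 9/8 = 112.5% for an early Visit 9, and one infusion is counted in two periods.

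None of these gives 100% for complete dosing across 3 days either side of target.

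**The case against.** The strongest objection is that Section 7.2 leaves the exit date undefined, so the 88.9% rests on an end date taken from Section 2. The neighbouring Section 7.1 measures exposure from first to last dose taken, inclusive; with the last dose as exit, on-target patients score 100%. It is fair that the term is undefined. But Section 2 is where the SAP says when the open-label period ends, and the last-dose reading goes above 100% as soon as that dose is 1 to 3 days early.

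Second, rounding up rests on the bracket symbols alone; no sentence says so. With plain brackets, Visit 9 on target would give 8/(57/7) = 98.2% and Visit 17 would give 16/(113/7) = 99.1%. The text at hand shows ceiling brackets, and plain brackets would still miss 100%.

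Third, the averages above are not those of the table to be reported. Open-label compliance is summarized for everyone who received an open-label dose, and Section 13 expects 40% of enrolled patients to qualify for randomization. If all other patients were scored correctly (an assumption), the table mean would fall by about 0.4 × 8.0 = 3.2 points with all transitions on target, or 0.4 × 4.6 = 1.8 points with uniform timing. This stands as a limit on size.

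Fourth, Section 7.1 separately summarizes treatment duration and number of infusions without this formula, so a reader has another view of dosing. This also stands, and it supports rating the point as minor.

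**Conclusion.** The point holds. Under the SAP's own period boundaries and visit targets, the Section 7.2 formula returns 9 to 17 expected open-label infusions where 8 to 16 are possible, whenever a patient moves to the DBTP on the target day or 1 to 3 days late. Complete dosing then scores 88.9% (Visit 9) to 94.1% (Visit 17).

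This rests on the exit date being the first double-blind dose, on rounding up as shown, and on one open-label infusion at each weekly visit before the transition. The averages also rest on the stated weights and timing.

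The point is minor. It concerns patients who enter the DBTP and a descriptive open-label table; no analysis population or hypothesis test uses the measure. No claim is made for the DBTP. The same excess would arise there only if no infusion is given at Visit 122/ET, which the SAP does not state, and the exit falls on or just after a weekly target day.

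**What to change.** In Section 7.2, define the period exit date and replace the elapsed-time formula with a count. Expected infusions are the scheduled infusion visits of that period's product from the entry visit up to, but not including, the exit visit. The exit visit counts only if an infusion of that period's product is scheduled there. For an exit between visits, count all scheduled infusion visits before it.

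Under perfect dosing this gives 8 expected for a transition at Visit 9 and 16 at Visit 17, whether early, on target or late. It also handles early withdrawal: exit on Days 2–4 gives 1 expected with 1 received, and exit on Days 9–11 gives 2 with 2. Rounding (exit − entry)/7 to the nearest whole number is a weaker substitute. It returns 8 and 16 within 3 days of target, but an exit on Day 2 gives 1/7, which rounds to 0 expected with 1 received.

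The cost is one or two sentences of SAP text and one derivation change. The count relies on the infusion schedule already set for the trial. No new data are needed, and no dose or clinical rule changes.
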